10.3.4. Missing Data Handling

Unless otherwise specified, missing data will not be imputed and will be excluded from the associated analysis.

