4.4. Withdrawal Criteria

All subjects have the right to withdraw at any point during treatment without prejudice. The investigator can discontinue any subject at any time if medically necessary. It will be documented whether or not each subject completed the clinical study. If for any subject study treatment or observations were discontinued, the reason will be recorded and the Sponsor should be notified promptly. Reasons that a subject may discontinue participation in a clinical study are considered to constitute one of the following:

- AE
- Death
- Subject withdrew consent
- Physician decision
- Lost to follow-up

Upon occurrence of a serious or intolerable AE, the investigator or designee will make every possible attempt to confer with the Sponsor before discontinuing the subject, and the DMC will be notified.

It is imperative to obtain complete follow-up data for all randomized subjects whether or not they receive their assigned treatment or have discontinued study drug. Every attempt should be made to collect follow-up information except for those subjects who specifically withdraw consent release of such information. All procedures and laboratory specimens or tests requested for evaluation following administration of the Study Drug should be carried out when possible

whether or not a subject continues to receive treatment according the protocol. Subjects will not be replaced in this trial.

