10. STATISTICAL PLAN

10.1. Sample Size

The sample size calculation was performed with the assumption (which was based on the observed results from a Phase I trial) that the difference in change from baseline between the active dose groups and the placebo group for LDL-C will be no less than 30 mg/dL, with a standard deviation of 20 mg/dL, using a Dunnet multiple t-test procedure for six comparisons.

Assuming about a 15% drop out rate, the sample size will be approximately 100 evaluable subjects total across the placebo groups and approximately 50 subjects in each of six ALN-PCSSC treatment groups. This sample size of at least 400 evaluable subjects will provide more than 90% power to detect a 30% reduction of LDL-C levels in at least one ALN-PCSSC dose group.

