10.3.2.1. Intent-to-Treat (ITT) Population

All subjects randomized into the trial. Treatment classification will be based on the randomized treatment. This population will be used to assess the randomness of treatment allocation.

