10.3.2.2. Modified Intent-to-Treat (mITT) Population

All randomized subjects who receive at least one dose of study drug and have both the baseline and the 180 day follow-up LDL-C assessment. Treatment classification will be based on the randomized treatment. This will be the primary population for analysis of the primary and secondary endpoints.

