10.3.2.3. Per-Protocol (PP) Population

All mITT subjects who received all randomized treatments and the 180 day follow-up LDL-C assessment. The PP population will be finalized during a data review before database lock. This will be the supportive population for analysis of the primary and secondary endpoints.

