10.4.3. Efficacy Analysis

10.4.3.1. Primary Efficacy Endpoints

The primary endpoint is the percentage change in LDL-C from baseline to Day 180.

Two sample t-tests will be performed to test the superiority of any dosing group over placebo. A Dunnett multiple t-test procedure will be applied to adjust for multiple comparisons with six different dosing regimens.

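### The primary LDL-C test leaves out dosed subjects without a Day 180 value and ignores their earlier measurements, which biases the treatment difference if response-related dropout is unequal between arms

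*Protocol*

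**What the plan says.** - **Primary set.** Protocol 10.3.2.2 defines the mITT population as "All randomized subjects who receive at least one dose of study drug and have both the baseline and the 180 day follow-up LDL-C assessment". It adds: "This will be the primary population for analysis of the primary and secondary endpoints". SAP 5.3.2.2 has the same definition.
- **Primary test.** Protocol 10.4.3.1 takes percentage change in LDL-C at Day 180 as the endpoint and states: "Two sample t-tests will be performed to test the superiority of any dosing group over placebo". A Dunnett adjustment covers the six regimens. SAP 5.4.4.1 agrees.
- **Missing data.** Protocol 10.3.4 and SAP 5.3.4 say that "missing data will not be imputed and will be excluded from the associated analysis". This is a default that allows exceptions, but neither document makes one for the primary endpoint.
- **Other sets.** The per-protocol set is "All mITT subjects who received all randomized treatments and the 180 day follow-up LDL-C assessment", so it has the same restriction. The ITT set has no efficacy role: "This population will be used to assess the randomness of treatment allocation".
- **Expected loss.** Protocol 10.1: "Assuming about a 15% drop out rate".
- **Follow-up.** Protocol 4.4: "It is imperative to obtain complete follow-up data for all randomized subjects".
- **Earlier LDL-C.** The schedule (Protocol Table 3) measures LDL-C at Days 14, 30, 60, 90, 120 and 150 in all arms, and at Day 104 in two-dose subjects only. These values serve only secondary endpoints, which the synopsis describes as descriptive.
- **SAP section 7** declares no changes to the protocol's analyses.

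**The concern.** Every planned efficacy analysis is conditional on having a Day 180 LDL-C. A subject last seen at Day 150 contributes nothing to the primary result, although that subject has six post-baseline values (seven in a two-dose arm). There is no repeated-measures model, no imputation and no missing-data sensitivity analysis to show whether this matters.

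Superiority over placebo is close to certain under the plan's own assumptions. The useful output is therefore the size of the Day 180 effect in each regimen, since Protocol 1.3.1 and SAP 5.4.4 say the results will guide the choice of dose for later studies. If poor responders leave one regimen more often than they leave placebo, that regimen looks better than it is. Such dropout is conceivable. Subjects enter with LDL-C above threshold, Protocol 5.2.1 bars adding LDL-lowering drugs, physician decision is a listed reason for discontinuation, and neither document says that on-study lipid results are withheld from sites.

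**Working it through.** **1. The plan's own figures.**

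Dropout: 480 × 0.85 = 408; 60 × 0.85 = 51 per active arm; 120 × 0.85 = 102 on placebo. Working back, 50/0.85 = 58.8 and 100/0.85 = 117.6, consistent with randomizing 60 and 120. Expected exclusions are 480 − 408 = 72.

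Power: difference 30, SD 20, 50 versus 100 evaluable, six Dunnett comparisons. The documents give no alpha; two-sided 0.05 is assumed, which gives a critical value of 2.617.

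Noncentrality = 30 / [20 × √(1/50 + 1/100)] = 30 / 3.464 = 8.66.

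Power exceeds 99.9% for each dose. It stays at or above 90% per dose up to an SD of about 44. The stated figure of more than 90% is reproduced, with the 15% loss already included.

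**2. Precision.** Assumed SD is 20 percentage points. The plan's 20 is in mg/dL, which equals 20 points only at a baseline of 100 mg/dL.

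- No missing data: 20 × √(1/60 + 1/120) = 3.16.
- Day 180 values only: 20 × √(1/51 + 1/102) = 3.43.
- Likelihood analysis that also uses a Day 150 value with correlation ρ to Day 180: 3.43 × √(1 − 0.15ρ²).

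| ρ | Likelihood SE | Excess of 3.43 over it |
|---|---|---|
| 0.5 | 3.37 | 1.9% |
| 0.7 | 3.30 | 3.9% |
| 0.85 | 3.24 | 5.9% |

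This is the best case, in which every lost subject is seen at Day 150. If the last value is at Day 60 and the monthly correlation is 0.5, then ρ = 0.5⁴ = 0.0625 and the excess is 1/√(1 − 0.15 × 0.0625²) − 1, about 0.03%. The range is therefore about 0 to 6%.

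**3. Bias.** Simulation of 60 active versus 120 placebo at seven visits, SD 20 points, true difference −38. Dropout log-odds depend on the last observed value in the active arm only, with 15 to 20% dropout. Correlations, slopes and the −38 are assumptions. Dropout is tied to within-arm response here, so the −38 does not affect the bias.

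| Monthly correlation | Slope per SD | Overstatement, Day 180 values only |
|---|---|---|
| 0.85 | 0 | none (mean −38.0) |
| 0.85 | 0.5 | about 1.1 (mean −39.1) |
| 0.85 | 1.0 | about 2.4 to 2.7 (mean −40.6 in one run) |
| 0.5 to 0.7 | 0.5 to 1.0 | about 0.3 to 1.5 |

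The likelihood estimate stayed within about 0.1 of the truth.

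**4. When the bias cancels or reverses.** A two-visit simulation with true difference −30, SD 20 and correlations 0.5/0.7/0.85 gave:

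- Same within-arm dependence in both arms: about −30.0 throughout. The difference is unbiased, although each arm's mean is shifted.
- One absolute-response rule in both arms (about 1.5% dropout on active, 10% on placebo): −29.1/−28.6/−28.4, an understatement of 0.9/1.4/1.6.

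**5. A ceiling.** If exactly the worst 15% at Day 150 left one arm only, the bias would be 20ρ × φ(z)/0.85, where z is the 15th percentile point. With φ(z) = 0.233 this is 5.49ρ, or 2.7, 3.8 and 4.7 for ρ = 0.5, 0.7 and 0.85. No one would expect selection that sharp.

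**The case against.** The strongest reply is that nothing in the documents shows dropout will be informative, let alone unequal. The trial is double-blind. Dosing is on Day 1, or on Days 1 and 90, so there is little continuing treatment to abandon. Lack of efficacy is not among the discontinuation reasons in Protocol 4.4. Follow-up continues after study drug is stopped, and Protocol 12.3 requires an explanation for a missed Day 180 assessment. The 15% is a planning allowance already in the sample size. Dose choice also draws on the Day 90 interim analysis and on safety. Finally, the likelihood method looks unbiased in the simulation because dropout was made to depend on observed values.

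Much of this stands. The mechanism is hypothetical, the bias at moderate slopes is below one standard error (2.7 against 3.43), and a check for dropout that depends on unobserved values is needed. It does not answer the main point: for subjects who do lack a Day 180 value, the plan discards relevant data and offers no way to judge the consequence.

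A reader might infer three stronger things that the documents do not support:

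- **That any dropout related to LDL-C response biases the comparison.** It does not; equal within-arm dependence cancels.
- **That power is at risk.** It is not; see the power figure above.
- **That subjects who stop treatment are excluded.** A subject who misses the second injection but has a Day 180 LDL-C stays in mITT.

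**Conclusion.** The point holds in a limited form. The primary analysis excludes dosed subjects without a Day 180 LDL-C, about 72 of 480 at the planned dropout, and uses none of their earlier values. The contrast with placebo is biased only if response-related dropout differs between arms or follows an absolute LDL-C level, and in the second case the effect may be understated.

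The 0.3 to 2.7 point overstatement rests on an assumed SD of 20 points, active-arm-only slopes of 0.5 to 1.0 per SD, and monthly correlations of 0.5 to 0.85. The documents supply none of these for percentage change. The precision loss is small. The reason to act is that the regimen-specific estimates can be protected against one plausible kind of dropout with data the trial already collects.

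**What to change.** 1. **Protocol 10.3.2.2 and SAP 5.3.2.2:** define the primary efficacy set as all dosed randomized subjects with a baseline and at least one post-baseline LDL-C. Without this edit a new model would still run on the same restricted set.
2. **Protocol 10.4.3.1 and SAP 5.4.4.1:** make the primary analysis a repeated-measures model of percentage change in LDL-C at Days 14, 30, 60, 90, 120, 150 and 180, with treatment-by-visit terms and an unstructured covariance. Leave out Day 104, which only two-dose subjects have. Take six Dunnett-adjusted Day 180 contrasts against pooled placebo.
3. **Protocol 10.3.4 and SAP 5.3.4:** name this model as the exception to the no-imputation, exclude-if-missing default.
4. **Sensitivity analyses:** keep the Day 180 observed-case t-test, and add one missing-not-at-random analysis, for example delta-adjusted or placebo-based imputation.
5. **SAP section 7:** if only the SAP can still be changed, record the departure from the protocol there.

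The cost is wording and a little more programming, with no new data. The model relies on missing-at-random, which is a weaker assumption than the present analysis makes; the fourth step tests departures from it.

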10.4. Statistical Analyses

10.4.1. Demographic and Background Characteristics

Subject demographics and baseline characteristics (including medical history) will be summarized by treatment group using the ITT, mITT, PP, and safety populations.

10.4.2. Study Drug and Concomitant Medications

Summaries of each prior (pre-baseline) medication and concomitant (baseline or later) medication will be provided by treatment. Separate summaries will be provided for prior

medication use. Medications will be coded using the WHO drug dictionary. Subjects will be counted only once within each period by medication.

10.4.3. Efficacy Analysis

10.4.3.1. Primary Efficacy Endpoints

The primary endpoint is the percentage change in LDL-C from baseline to Day 180.

Two sample t-tests will be performed to test the superiority of any dosing group over placebo. A Dunnett multiple t-test procedure will be applied to adjust for multiple comparisons with six different dosing regimens.

10.4.3.2. Secondary Efficacy Endpoints

The secondary objectives of this study are to evaluate the effect of ALN-PCSSC on the following:

- Percentage change in LDL-C from baseline to Day 90
- Percentage change in LDL-C from baseline to Days 14, 30, 60, 104, 120, 150, and 210
- Proportion of subjects in each group with LDL-C greater than 80% of the baseline value at Day 180 and Day 210
- Duration of time on treatment for subjects to return to 80% of baseline or greater LDL-C or PCSK9 protein
- Individual responsiveness defined as the number of subjects reaching on treatment LDL-C levels of <25 mg/dL, <50 mg/dL, 70 mg/dL, and <100 mg/dL at Days 90, 120, and 180
- Proportion of subjects in each group with greater or equal to 50% LDL-C reduction from baseline at Days 90, 120, and 180
- Percentage change in PCSK9 levels from baseline to Days 14, 30, 60, 90, 104, 120, 150, 180, and 210
- Percentage change in other lipids, lipoproteins, and apolipoproteins from baseline at each subsequent visit to Day 210
- Proportion of subjects in each group who attain global lipid modification targets for their level of ASCVD risk

10.4.3.3. Interim Analysis

An interim analysis of lipids and PCSK9, unblinded by dose cohort only, will be prepared upon completion of Day 90 by the Statistical Reporting Organization. The interim analysis will be performed for all subjects completing Day 90 and these data will be used to help select the ALN-PCSSC dose for subsequent clinical trials.

10.4.4. Safety Analysis

The safety objectives of this study are to evaluate the safety and tolerability profile of ALN-PCSSC.

10.4.4.1. Adverse Events

The Medical Dictionary for Regulatory Activities (MedDRA) dictionary will be used for coding AEs. An AE (classified as preferred term) occurring during the double-blind treatment period will be counted as a treatment emergent AE (TEAE) either if it is not present at baseline or if it is present at baseline but increased in severity during the treatment period.

The number (percentage) of subjects reporting TEAEs for each preferred term will be tabulated by system-organ class, by system-organ class and severity, and by system-organ class and relationship to study drug. If more than one event occurred with the same preferred term for the same subject, the subject will be counted only once for that preferred term using the most severe or related occurrence for the summary by severity, or relationship to study drug, respectively.

Incidences of injection site reactions will also be presented by dose group (see also [Section 8.1.4](#)). Time to first injection site reaction will be analyzed. The severity and duration of injection site reactions, as well as their signs and symptoms, will also be summarized.

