 - e. Involved with, or a relative of, someone directly involved in the conduct of the study.
 - f. Any known cognitive impairment (eg, Alzheimer's disease).
17. Previous or current treatment (within 90 days of screening) with monoclonal antibodies directed towards PCSK9.

**For the entire duration of the study

Subjects excluded for any of the above reasons may not be re-screened for participation at any time if the exclusion characteristic has changed.

Test Product, Dose and Mode of Administration: ALN-PCSSC will be administered as either a single SC injection (doses: 200 mg, 300 mg), or two injections (dose: 500 mg) on Day 1 or two SC injections (doses: 100 mg, 200 mg, or 300 mg) on Day 1 and Day 90.

Duration of Treatment: The expected duration of the subjects' involvement in the study will be approximately 224 days which includes screening, study drug administration, the course of single or multiple injections, and the follow-up period to Day 210; if additional follow-up is necessary, the expected maximum duration of involvement in the study will be 374 days.

Single Dose (one or two injections on Day 1):

- Screening: Day -14 to -1
- Randomization, initiation of study drug: Day 1
- Treatment Phase: Day 1
- Follow-up:
 - Follow-up: Days 2 to 210; EOS on Day 210
 - Additional Follow-Up (for subjects in whom LDL-C levels have not returned to >80% of baseline values; subjects will return each month for follow-up until this level has been reached or until Day 360): Days 240, 270, 300, 330, and 360

Two Doses (one injection each on Day 1 and Day 90):

- Screening: Day -14 to -1
- Randomization, initiation of study drug: Day 1
- Treatment Phase: Day 1 to Day 90
- Follow-up:
 - Follow-up: Days 91 to 210; EOS on Day 210
 - Additional Follow-Up (for subjects in whom LDL-C levels have not returned to >80% of baseline values; subjects will return each month for follow-up until this level has been reached or until Day 360): Days 240, 270, 300, 330, and 360

Reference Therapy, Dose, and Mode of Administration: Placebo will be administered as either one or two SC injections of saline solution. Placebo volume will be matched to test product volume within each dose and injection regimen but not between injection regimens. For example, the placebo group for the 200 mg dose will receive 1.0 mL of placebo whereas the placebo group for the 300 mg dose will receive 1.5 mL of placebo.

Criteria for Evaluation:

Efficacy:

Primary Endpoint:

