1.3.2. Dose Rationale

Previous studies using PCSK9-targeting siRNAs formulated in LNPs (ALN-PCS02) or using PCSK9 antibodies, and one Phase I study with ALN-PCSSC in which subjects received single-doses ascending from 25 mg to 800 mg, have demonstrated that substantial lowering of PCSK9 is safe and well-tolerated in humans. Doses for the Phase I study were calculated using the rat and monkey no observed adverse effect levels (NOAELs) based on body weight and body surface area (mg/m²). Collectively, the results of nonclinical studies with ALN-PCSSC supported a starting dose of 25 mg for subjects participating in the SAD phase of the previous Phase I study.

In Phase I Study ALN-PCSSC-001, clinically significant reductions in LDL-C levels were seen with single ALN-PCSSC doses as low as 25 mg with larger decreases seen with higher doses and a plateau at 300 mg. Subjects at ALN-PCSSC doses of 300 mg or higher had maximal LDL-C reductions of up to 78.1% and average least squares mean group nadir reductions of 50 to 59%. In the MD phase, 45 subjects received multiple doses of either ALN-PCS (125 mg weekly x4, 250 mg biweekly, 300 mg and 500 mg twice given 1 month apart) or placebo. Subjects at ALN-PCSSC doses of 300 mg or higher had maximal LDL-C reductions of 83% and average least squares mean group nadir LDL-C reductions of 53.4% to 59.9% at all dose levels tested.

Based on the interim results of the Phase I Study ALN-PCSSC-001, where maximum effect on LDL-C was seen by 84 days and a significant effect was still observed at 180 days, the Phase II study has been designed to test the efficacy of a single dose (200 mg, 300 mg, or 500 mg) or two doses 90 days apart (100 mg, 200 mg, or 300 mg). This will allow dose selection for Phase III. The dosing regimens used in Phase II are therefore fully supported by the findings of the Phase I study.

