6. SCHEDULE AND SEQUENCE OF PROCEDURES

The Schedule of Events/Assessments ([Table 3](#)) summarizes the study assessments by time point. This study consists of 10 (one dose) or 11 (two doses) visits and four phases:

Single Dose (one or two injections on Day 1):

- Screening: Day -14 to -1
- Randomization, initiation of study drug: Day 1
- Treatment Phase: Day 1
- Follow-up:
 - Follow-up: Days 2 to 210; end of study (EOS) on Day 210
 - Additional Follow-Up (for subjects in whom LDL-C levels have not returned to >80% of baseline values; subjects will return each month for follow-up until this level has been reached or until Day 360): Days 240, 270, 300, 330, and 360

Two Doses (one injection each on Day 1 and Day 90):

- Screening: Day -14 to -1
- Randomization, initiation of study drug: Day 1
- Treatment Phase: Day 1 to Day 90
- Follow-up
 - Follow-up: Days 91 to 210; EOS on Day 210
 - Additional Follow-Up (for subjects in whom LDL-C levels have not returned to >80% of baseline values; subjects will return each month for follow-up until this level has been reached or until Day 360): Days 240, 270, 300, 330, and 360

The expected duration of the subjects' involvement in the study will be approximately 224 days, which includes screening, study drug administration, the course of one or two injections, and the follow-up period to Day 210.

Subjects whose LDL-C levels have returned to baseline levels and who have completed the study to Day 210 will be given the opportunity to enroll in a separate long-term extension study in order to collect long-term efficacy and safety data.

Any subjects in whom LDL-C levels have not returned to >80% of baseline values by Day 210 will continue to be followed on a monthly visit schedule as part of this study until either this level has been reached or a maximum of Day 360 at which point they will be given the opportunity to enroll in the long-term extension study. At each visit, LDL-C levels, AEs, SAEs, concomitant medications, and safety laboratory assessments will be collected. For these subjects, the expected maximum duration of involvement in the study will be 374 days.

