5.4.5.1. Adverse Events

The Medical Dictionary for Regulatory Activities (MedDRA) dictionary will be used for coding AEs. An AE (classified as preferred term, and AESI) occurring during the double-blind treatment period will be counted as a treatment emergent AE (TEAE) either if it is not present at baseline or if it is present at baseline but increased in severity during the treatment period.

The number (percentage) of subjects reporting TEAEs for each preferred term will be tabulated by system-organ class, by system-organ class and severity, and by system-organ class and relationship to study drug. If more than one event occurred with the same preferred term for the same subject, the subject will be counted only once for that preferred term using the most severe or related occurrence for the summary by severity, or relationship to study drug, respectively.

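### The window for counting treatment-emergent AEs has no dates in either document, and none of the stated intervals that could supply them gives one sound window for all arms

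*Protocol*

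**What the plan says.** Protocol 10.4.4.1 counts an AE as treatment-emergent if it is new and is one "occurring during the double-blind treatment period will be counted as a treatment emergent AE (TEAE", or "if it is present at baseline but increased in severity during the treatment period". SAP 5.4.5.1 uses the same rule and extends it to AEs of special interest: "An AE (classified as preferred term, and AESI) occurring during the double-blind treatment period". Neither section gives days.

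The only treatment interval with days attached is the Treatment Phase in the phase lists (Protocol synopsis, Protocol 6, SAP 1.4):

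- One dose: "Treatment Phase: Day 1", then "Follow-up: Days 2 to 210; end of study (EOS) on Day 210".
- Two doses: "Treatment Phase: Day 1 to Day 90", then "Follow-up: Days 91 to 210; EOS on Day 210".

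Three other places bear on the window. Protocol 8.2 has AEs recorded from randomization to end of study, and to as late as Day 360 in subjects whose LDL-C has not recovered. Protocol 10.3.3 and SAP 5.3.3 make LDL-C recovery above 80% of baseline the last observation and drop later safety events from the planned analysis. Protocol 10.4.4.4 and SAP 5.4.5.5 plan a summary of treatment-emergent neurological abnormalities. SAP Section 7 reports no change from the protocol, so the SAP does not settle the question.

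**The concern.** Someone programming the AE tables needs a first and a last day. The nearest dated interval is the Treatment Phase, and it fits the purpose badly. It ends on the day of injection for one-dose regimens and at Day 90 for two-dose regimens, while Protocol 1.3.2 reports from Phase I that "a significant effect was still observed at 180 days".

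Safety and tolerability is a stated objective, and SAP 5.4.4 says efficacy and safety results will help choose the Phase 3 dose or doses. That choice includes one-dose against two-dose regimens. If the counting window differs between regimens, the regimen with the longer window will show more treatment-emergent AEs for that reason alone. If the window stops at Day 90 for everyone, nearly all the time after the second injection is missing from the main tables.

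**Working it through.** **Inputs.** Screening is 14 days, end of study is Day 210 and the last additional visit is Day 360 (Protocol 6). Table 1 gives three one-dose and three two-dose regimens, each with 60 active and 20 placebo subjects, so 240 subjects per schedule.

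**The plan's own durations.** 14 + 210 = 224 days and 14 + 360 = 374 days. Both match Protocol 6, so 210 days is the right denominator.

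**Share of days covered = window days / 210.**

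| Reading of the treatment period | One dose | Two doses | Left out |
|---|---|---|---|
| A. Treatment Phase in the phase lists | 1/210 = 0.5% | 90/210 = 42.9% | 99.5% and 57.1% |
| B. Table 3 header as extracted (to Day 90 for both) | 90/210 = 42.9% | 90/210 = 42.9% | 120/210 = 57.1% |
| C. Up to the last observation | ends at LDL-C recovery | ends at LDL-C recovery | varies by subject and arm |
| D. First injection to Day 210 (stated nowhere) | 210/210 = 100% | 210/210 = 100% | none |

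**Pooled over 480 subjects, reading A.** Covered person-days are 240 × 1 + 240 × 90 = 21,840. Planned person-days are 480 × 210 = 100,800. The ratio is 21.7%.

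**What window length alone does, reading A.** Assume, for illustration only, a constant hazard and a true incidence *p* by Day 210 that is the same in every arm. The expected proportion counted in a window of *w* days is 1 − (1 − *p*)^(*w*/210).

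| Assumed *p* by Day 210 | One dose (*w* = 1) | Two doses (*w* = 90) |
|---|---|---|
| 10% | 0.05% | 4.4% |
| 30% | 0.17% | 14.2% |
| 50% | 0.33% | 25.7% |
| 70% | 0.57% | 40.3% |

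Reactions that cluster just after an injection would be captured better than this, and late events worse. The documents give no event timing, so the table shows direction and scale only.

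**Which comparisons are affected.** Under A, each placebo subset follows its active group's schedule, so an active group and its matched placebo have equal windows. Comparisons between one-dose and two-dose regimens do not. The AE sections do not say whether placebo is pooled. If it is, 60 placebo subjects would carry a 1-day window and 60 a 90-day window. Under B, windows are equal but short. Under C, a placebo subject whose LDL-C hardly moves can meet the recovery criterion at the first post-dose visit, while an active subject may not meet it for months, so windows differ between active and placebo.

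**Two checks inside the documents.** Table 3 allows ±3 days at the Day 90 visit, so a second injection on Days 91 to 93 would fall outside the Treatment Phase under A or B, together with any reaction that day. The only scheduled post-baseline neurological examination is at end of study; if treatment-emergent has the same meaning there, no finding from a Day 210 examination could qualify under A or B.

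**The case against.** A reader might infer that the documents fix the window at Day 1 and Days 1 to 90. They do not. The AE sections speak of a treatment period and the phase lists of a Treatment Phase, and nothing equates the two. The phase lists describe dosing and visits; they are not analysis windows. Several places point to a longer window:

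- AEs are recorded to end of study (Protocol 8.2).
- Protocol 3.4 speaks of on-treatment LDL-C at Days 90, 120 and 180 in all groups, including the one-dose regimens.
- A planned neurological summary that would be empty for completers under the short readings suggests that those readings were not meant.
- Excluding safety events after the last observation would be almost pointless if one-dose events already stopped counting after Day 1.

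All of this stands as evidence of intent, but it does not supply a rule. Protocol 10.3.3 names an observational period reaching the end-of-study visit, but that period starts at screening and is followed at once by the LDL-C cut-off. The cut-off may have been meant only for additional follow-up after Day 210; the text does not limit it that way. The synopsis heading on duration of treatment spans 224 days, but includes screening.

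Two further stronger readings also fail. Missing 57% or 99.5% of days is not the same as missing that share of events. Nor are events lost from the record: all data go into listings, the data monitoring committee reviews safety every 2 months, and injection site reactions have their own summaries of incidence, time to first event, severity and duration.

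**Conclusion.** The point holds as an undefined window with conflicting candidates. The treatment-emergent AE tables cannot be programmed unambiguously from either document, and each interval that the documents do state gives a poor window. The phase lists cover 0.5% or 43% of the 210 days and treat regimens unequally. The Table 3 header covers 43% for all. The last-observation rule can give placebo a shorter window than active drug.

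The claim that the plan restricts treatment-emergent AEs to Day 1 or Days 1 to 90 goes further than the text allows, as does any claim of bias between an active group and its own matched placebo under the phase reading. The Table 3 reading depends on a header extracted from PDF and is uncertain. The probable intention was a window to end of study, so the plan should be made to say so. This should be fixed before database lock; confidence is moderate.

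**What to change.** 1. In Protocol 10.4.4.1 and SAP 5.4.5.1, define the treatment-emergent window, for both onset and worsening, as first injection through the Day 210 end-of-study visit (or withdrawal) in every arm. Ending at the visit as attended keeps in findings made within its ±3-day allowance.
2. State that the same window applies to treatment-emergent neurological findings (Protocol 10.4.4.4, SAP 5.4.5.5).
3. Tabulate AEs from the Day 240 to 360 visits separately. Those subjects are selected by LDL-C that has not recovered, so their extra time is not comparable across arms.
4. Amend Protocol 10.3.3 and SAP 5.3.3 so that the LDL-C recovery cut-off does not apply to safety events up to Day 210. Without this, item 1 would contradict the existing cut-off.

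A split of the two-dose tables at the second injection is a useful option.

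The cost is wording in a few sections of each document. AEs are already collected to Day 210, so no new data or change in conduct is needed. Reported treatment-emergent AE rates will be higher than under the shorter readings.
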